Methods. To increase physical activity for Veterans with PTSD, this project will combine GET, motivational interviewing, and mobile health technology (mHealth) to address attitudinal and behavioral barriers particularly relevant for this group. First, we will work collaboratively with our Veteran Engagement Panel to adapt GET protocols effective for non-PTSD populations (eg, adults with chronic pain or fatigue), and incorporate motivational interviewing and mHealth. We will then pilot test the intervention in 3 consecutive groups of 6-8 participants (total n=18-24) and use concurrent mixed-methods to examine feasibility and acceptability. Quantitative measures will include recruitment (proportion enrolled out of total eligible); attendance (proportion who attend 75% of in-person visits); and retention (proportion who complete data collection post-intervention). Qualitative assessments will involve semi-structured interviews on acceptability of

intervention components (eg, session formats and topics, usability of mHealth), and barriers and facilitators to attendance. At baseline, during and post-intervention, we will also assess overall and physical functioning using Veterans RAND 36-item, 6-minute walk, and 30-second sit to stand, and collect additional data (PTSD symptoms, depression, pain, fatigue, and sleep quality) to inform a future randomized trial.

List of Abbreviations

CCDOR.....	Center for Care Delivery & Outcomes Research
CBT	Cognitive Behavioral Therapy
Co-I.....	Co-Investigator
ED.....	Emergency Department
GET	Graded Exercise Therapy
HSRD	Health Services Research and Development
IRB.....	Institutional Review Board
mHealth	Mobile Health Technology
MVAHCS	Minneapolis VA Health Care System
NIH	National Institutes of Health
PACT	Patient Aligned Care Team (VA primary care staff)
PCMHI	Primary Care Mental Health Integration
PCL-5	PTSD symptom checklist for the DSM-5
PC-PTSD-5.....	Primary Care Screen for PTSD for DSM-5
PEG	Brief 3-item Scale on Pain Intensity & Interference
PHQ-9.....	Patient Health Questionnaire-9
PI	Principal Investigator
PSQI	Pittsburgh Sleep Quality Index
PTSD	Posttraumatic Stress Disorder
PT.....	Physical Therapist
RR&D	Rehabilitation Research and Development
UMN	University of Minnesota
VA.....	Department of Veterans Affairs
VHA	Veterans Health Administration
VINCI.....	VA Informatics and Computing Infrastructure
VR-36	Veterans RAND 36-item Health Questionnaire
WRAP.....	Wearables Research and Analytics Platform

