3.0 OBJECTIVES

The overall objectives of this study are to develop and pilot test a novel intervention aimed at initiating and maintaining higher levels of physical activity for Veterans with PTSD.

Aim 1: Adapt GET and incorporate motivational interviewing and mHealth to increase physical activity and improve physical functioning for Veterans with PTSD. We will develop treatment manuals, training procedures for physical therapists (as interventionists), and processes for fidelity assessment.

Aim 2: Conduct a pilot study to examine feasibility and acceptability of the intervention for a future randomized controlled trial. We will pilot test the intervention in 3 consecutive groups of 6-8 participants (total n=18-24) and use concurrent mixed-methods to examine feasibility and acceptability. We expect 75% attendance and retention, based on results from pilot studies of group exercise interventions for PTSD (eg, retention of 76-82%).^{25, 26}

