RTI will provide weekly data to the VA study team, and once obtained, these data will be stored behind the VA firewall (see section below on protection of participant privacy for full description of information security procedures). VA study staff may review participants' physical activity and sleep data via the company website, in order to provide feedback to participants on their progress. RTI will also assist with generating weekly activity summary progress reports for participants. These will include physical activity data to provide updates on participants' progress towards their activity goals (eg, minutes of walking or biking per day). The reports may display physical activity data using graphs and other figures available through the device company accounts (see Appendix 1). Additionally, reports will include messages of encouragement that are tailored to the participants' progress that week (Table 3). Finally, we will provide a short summary statement of financial incentives they should expect (eg, "You met your goals on 3 days during this past week. This means you will receive \$6."). In all communications with RTI (and materials sent by them), participants will be referred to by their dummy email & device identifier. RTI will not have access to any identifiable participant information.

Table 3. Examples of Tailored Messages

Group 1: Meeting daily activity goals \geq 5 days per week	Group 2: Meeting daily activity goals 3-4 days per week	Group 3: Meeting daily activity goals 0-2 days per week
You are on the right track!	. You will be on your way to a healthier new you!	New activities can be challenging to do. Take it one day at a time!
You are on your way to a healthier new you!	We know this is tough but keep at it!	We know it is not easy, but it is worth it! Tell a friend what you look forward to most!

b. Video-conferencing

Due to the COVID-19 pandemic and higher risk for group activities, we will conduct all group sessions and some individual meetings (see Appendix 2) via videoconferencing on Zoom, a VA and HIPAA compliant videoconferencing platform. VA ORD permits group meetings via platforms that are approved by the ISSO. Zoom is included in the VA Technical Reference Model (TRM), a list of VA-approved technologies. We will audio-record some sessions to assess intervention fidelity.

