We propose to conduct a pilot study of 3 groups with 6-8 participants each (total n=18-24). Based on our clinical and research experience with piloting group interventions, and number of participants in the active arm of recent pilot studies of group exercise interventions for PTSD,^{25, 26} we expect that 3 groups will provide sufficient data on feasibility and acceptability to inform a larger study. A control group will not be enrolled as examining efficacy is not appropriate at this stage,^{53, 54} and our main goal is to evaluate feasibility and acceptability of the active intervention. Co-Investigator [name] will be the PT interventionist conducting in-person assessments, video-conferencing sessions, and telephone calls. We will use a concurrent mixed-methods approach to assess feasibility and acceptability, and anticipate making protocol modifications as appropriate. Data on physical activity, functioning, and symptoms will also be collected, to determine feasibility of outcomes assessments for a future randomized trial.

1. Human Subjects Involvement & Characteristics.

We will screen Veterans being seen in-person or having virtual care appointments at MVAHCS primary care clinics for PTSD (ie, ≥3 on Primary Care Screen for PTSD-5) and self-reported health-related limitations in mobility (ie, climbing several flights of stairs or walking several blocks). Exclusion criteria include ongoing suicidal ideation or psychosis; medical contraindications to exercise (eg, complete paraplegia); high degree of disability (ie, impairments in ≥2 basic activities of daily living); plans to move out of the area permanently within 4 months; major neurocognitive impairment (eg, dementia), schizophrenia; acute mental health crisis within the past 3 months (requiring an ED visit or hospitalization); and routinely completing 150 minutes or more of moderate to vigorous activity per week. We will not recruit prisoners, institutionalized individuals, or children. Our goal is to conduct 3 groups of 6-8 participants each (18-24 total).

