The study coordinator will schedule a telephone call with Veterans to go over the informed consent form, HIPAA authorization form, and enrollment forms for financial incentives. We will also include other materials to describe the study (eg, FAQ document, expectations for confidentiality and privacy during group meetings, and troubleshooting Zoom). We will mail potential participants these materials ahead of the phone call, instructing them not to sign any forms until the call. During the call, the study coordinator will provide a thorough overview of study participation, risks, benefits, alternatives, protections, and IRB and study staff contact information. We will emphasize the voluntary nature of study participation and provide the opportunity for questions about the study. The consent process will be conducted by the study coordinator, who is trained in the ethics of human subject research. Those who agree to participate will mail back signed informed consent and HIPAA authorization forms via prepaid stamped envelopes. Signed informed consent and HIPAA authorization forms will be received by the study team before collection of any participant data.

5. Quantitative Data & Analyses (Table 4)

Feasibility will be quantitatively assessed as **recruitment** (proportion enrolled out of total identified as eligible), **attendance** (proportion who attend $\geq 75\%$ of in-person visits), and **retention** (proportion who complete post-intervention assessments). To determine feasibility, we will first evaluate recruitment and time needed to enroll participants. We anticipate approximately

20 Veterans per month may be eligible (based on preliminary data noted above), and with 20% recruitment, we expect to complete enrollment for each group in 4-6 weeks. We have set attendance and retention benchmarks at 75%, which are realistic estimates based on recent pilot studies of group exercise interventions for PTSD (participants attended an average of 78-82% of sessions and overall retention were 76-82%).^{25, 26}

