Appendix 2: Detailed Outline of Topics and Goals for Sessions

Week	Content and Goals
0	
Baseline In-Person Visit (95 min)
 
 • Assessments (30 min) 
 ○ Survey—Functioning, mental health symptoms, sleep, pain, & fatigue* ○ Physical Performance—6-minute walk, 30-second sit to stand, range of motion screen, strength screen, & 4-stage balance test • Introduction to rationale & I CARE schedule (20 min) 
 ○ Rating of perceived exertion (handout) • Motivational interviewing (20 min) 
 ○ Identify values & beliefs about physical activity ○ Develop discrepancy between current behavior and values ○ Readiness rulers—confidence & importance • Introduction to device, activity logs & financial incentives (20 min) 
 ○ Set up Garmin Vivosmart 4 & Garmin Connect Application ○ Instruct on completing activity logs & mailing back • Closing (5 min)
0.5	
Tech Prep Call (Virtual via Zoom, 30 min)
 
 • Mock session to introduce and troubleshoot Zoom platform issues
1	
Group Session #1 (Virtual via Zoom, 90 min)
 
 • Discussion #1 (30 min) 
 ○ Introductions, establish ground rules for group meetings (Expectations & Guidelines Handout) ○ Elicit participant goals for physical activity & health (Readiness Rulers) • Group exercise (25 min) • Discussion #2 (15 min) 
 ○ Participant experiences with group exercise, rating of perceived exertion ○ Graded steps to increase activity, time-based pacing (Graded Steps Handout) ○ I CARE video playlist, elicit other exercise options • Home exercise plan (15 min) 
 ○ Plan for week #1 (Home Exercise Worksheet; Readiness Rulers) ○ Share goals with group ○ Closing (5 min)
1.5	
Individual Session #1 (Virtual via Phone, 10-15 min)
 
 • MI: 
 ○ Readiness ruler ○ Self-efficacy, develop discrepancy ○ Amplify change talk, roll with resistance • Troubleshooting home activity plan 
 ○ Review safe space in home ○ Address level of activity, correct positions, etc.

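### The 75% attendance benchmark is a share of participants, but the evidence cited for it is a mean share of sessions, and the visits it counts are mostly no longer held in person

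*Combined protocol and SAP*

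**What the plan says.** Section 5.0 C.5 (Quantitative Data & Analyses) lists attendance as one of three quantitative feasibility measures and defines it as the "proportion who attend $\geq 75\%$ of in-person visits". The Methods paragraph of the abstract has the same measure: "attendance (proportion who attend 75% of in-person visits".

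C.5 then gives the target and its basis: "We have set attendance and retention benchmarks at 75%, which are realistic estimates based on recent pilot studies". The figures cited from those pilots are that "participants attended an average of 78-82% of sessions and overall retention were 76-82"%.

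Section 3.0 (Objectives) repeats the expectation but cites retention only: "We expect 75% attendance and retention, based on results from pilot studies of group exercise interventions for PTSD (eg, retention of 76-82"%.

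On delivery, section 5.0 B.4.b states that "we will conduct all group sessions and some individual meetings (see Appendix 2) via videoconferencing on Zoom". Appendix 2 labels two contacts as in-person: the week 0 baseline visit ("Baseline In-Person Visit (95 min") and the week 16 final assessment. The pilot has "3 groups with 6-8 participants each (total n=18-24").

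**The concern.** Two different quantities carry similar percentages. The benchmark concerns the proportion of people above a cut-off. The evidence is the average fraction of sessions attended. Nothing in the documents reports what proportion of the earlier pilots' participants reached 75%, so nothing links the two. The retention benchmark beside it does not have this problem, because a proportion retained is compared with proportions retained.

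Attendance is meant to inform a future randomized trial. If Veterans attended on average exactly as in the cited pilots, the trial could still report a missed benchmark because of the change of scale. Equally, a pass could not be read as matching those pilots.

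The denominator adds a second difficulty. The definition counts in-person visits, but the sessions whose attendance is of interest have moved to video.

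**Working it through.** **Inputs.** From C.5: per-person cut-off 75%, benchmark 75%, cited mean attendance m = 78-82%. From 5.0 C: n = 18-24. From Appendix 2: 4 group sessions (Zoom), 7 individual phone sessions, 2 in-person visits. Assumed, because the documents give no attendance distribution: the within-person correlation ρ. The plan gives no derivation of the 75%, so there is no figure to reproduce.

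**1. A mean does not fix the proportion (no model needed).** Take 24 participants and 4 sessions, with 14 people attending 4 and 10 attending 2.
- Mean = (14×4 + 10×2)/96 = 76/96 = 79.2%, inside the cited range.
- Share at or above 75% (3 or more of 4) = 14/24 = 58%.

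The smallest possible share q with 4 sessions occurs when those above the cut-off attend all 4 and the rest attend 2: q + 0.5(1 − q) = m, so q = 2m − 1. This gives 56% at m = 78% and 64% at m = 82%. The largest possible share is 100%.

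**2. Expected share over the 4 group sessions.** With independent sessions, P(X ≥ 3) = 4m³(1 − m) + m⁴.
- m = 0.78: 0.418 + 0.370 = 0.788
- m = 0.82: 0.397 + 0.452 = 0.849

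With correlated sessions, a beta-binomial is used with a = m(1 − ρ)/ρ and b = (1 − m)(1 − ρ)/ρ:

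| Mean | ρ = 0 | ρ = 0.3 | ρ = 0.5 | ρ = 0.9 |
|---|---|---|---|---|
| 78% | 79% | 75% | 75% | 77% |
| 82% | 85% | 80% | 80% | 81% |

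For ρ from 0 to 0.5 the range is about 75-85%.

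**3. Chance that the pilot observes at least 75%.** This needs 14 of 18 (0.75×18 = 13.5, rounded up) or 18 of 24. Binomial tail probabilities at the expected share:

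| Mean, ρ | Expected share | n = 18 | n = 24 |
|---|---|---|---|
| 78%, 0.3 | 75% | 52% | 61% |
| 78%, 0 | 79% | 67% | 77% |
| 82%, 0.3 | 80% | 72% | 81% |
| 82%, 0 | 85% | 88% | 94% |

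**4. The denominator as written.** With two in-person visits, attending one is 50%, so passing 75% means attending both. The second is the final assessment, whose completion is the definition of retention. Among people who come to baseline, attendance and retention are then almost the same variable. In section 5.0 C.6, the two planned theme comparisons (by attendance and by completion of post-intervention assessments) would split nearly the same people.

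**The case against.** The cited evidence comes from group exercise pilots, so the natural counterpart is the 4 group sessions. There the models give about 75-85%, and at ρ = 0.9 still 77-81%. On that reading 75% is roughly what a mean of 78-82% would produce. This stands, and it limits the point to missing support for the benchmark.

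A reader might infer something stronger: that a trial performing like its source should be expected to miss the benchmark. Other denominators seem to suggest so, with expected shares for ρ = 0-0.5 of 61-75% for the 2 in-person visits and 55-73% for 11 contacts (4 group plus 7 phone). The documents do not support that inference, for three reasons.
- The two in-person visits are assessments, so a session rate does not carry over. If nearly everyone attends baseline (an assumption), the cited retention of 76-82% is the better guide.
- With 11 contacts the cut-off becomes 9/11 = 82%. With 12 contacts (9/12 = 75% exactly) the same models give 69-85%, so part of the low figure is rounding. Phone contacts are also outside the stated definition.
- Stopping at ρ = 0.5 is a choice. At ρ = 0.9 the shares are 76-81% (2 visits) and 76-80% (11 contacts).

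It is also fair to say that no stop/go rule hangs on the benchmark, that interviews supplement it, and that protocol modifications are anticipated. One could read 75% as the per-person cut-off only. Then no target proportion is stated, and the cited mean supplies none.

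**Conclusion.** The point holds as a mismatch between a benchmark and its evidence. It is not an arithmetic error, and the documents do not show that the benchmark is too high. The mismatch itself is certain from the text of C.5. Its size is not: over 4 group sessions a mean of 78% is compatible with anything from 56% to 100% of people above the cut-off, and about 75-85% is expected for means of 78-82% under binomial and beta-binomial models with assumed correlations of 0-0.5. At the lower end of that range, meeting the benchmark is close to an even chance at n = 18 (52%) and 61% at n = 24. Separately, and without any model, the in-person denominator no longer describes the sessions delivered, and it makes attendance nearly a copy of retention.

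**What to change.** In section 5.0 C.5:
1. Replace the in-person denominator with a named list of scheduled sessions, for example the 4 group sessions.
2. Place the 75% benchmark on the mean percentage of those sessions attended, so that it can be compared with the cited 78-82%.
3. Report the proportion of participants attending at least 75% of the same sessions beside it, with an exact confidence interval and no benchmark.

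Make matching edits in the abstract (Methods), section 3.0 and section 5.0 C.6. The per-person cut-off can stay as the grouping variable in C.6, using the new denominator.

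Keeping the per-person benchmark and taking a new value from the models above is not advisable, because that value would rest on assumed correlations.

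Cost: the benchmarked attendance measure changes and a few sentences need editing. No new data are needed. Sampling error in a pilot of 18-24 remains on either scale.

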6.0 REPORTING

Any change in a participant's ability to engage in the physical activity program will be immediately reported by the PT interventionist to [name], the Principle Investigator and communicated to the participant's primary care team. If suicidal ideation is found upon initial eligibility screening by the study staff, they will immediately notify [name], who will undertake appropriate evaluations and clinical referrals. If participants are noted to have severe or worsening PTSD and/or depression symptoms, they will be offered referrals for mental health treatment at MVAHCS. Notably, given the additional clinical expertise of Co-Investigators in rehabilitation medicine and mental health, this study team is well prepared to handle any potential health concerns that may arise.

Appendix 2: Detailed Outline of Topics and Goals for Sessions

Week	Content and Goals
0	
Baseline In-Person Visit (95 min)
 
 • Assessments (30 min) 
 ○ Survey—Functioning, mental health symptoms, sleep, pain, & fatigue* ○ Physical Performance—6-minute walk, 30-second sit to stand, range of motion screen, strength screen, & 4-stage balance test • Introduction to rationale & I CARE schedule (20 min) 
 ○ Rating of perceived exertion (handout) • Motivational interviewing (20 min) 
 ○ Identify values & beliefs about physical activity ○ Develop discrepancy between current behavior and values ○ Readiness rulers—confidence & importance • Introduction to device, activity logs & financial incentives (20 min) 
 ○ Set up Garmin Vivosmart 4 & Garmin Connect Application ○ Instruct on completing activity logs & mailing back • Closing (5 min)
0.5	
Tech Prep Call (Virtual via Zoom, 30 min)
 
 • Mock session to introduce and troubleshoot Zoom platform issues
1	
Group Session #1 (Virtual via Zoom, 90 min)
 
 • Discussion #1 (30 min) 
 ○ Introductions, establish ground rules for group meetings (Expectations & Guidelines Handout) ○ Elicit participant goals for physical activity & health (Readiness Rulers) • Group exercise (25 min) • Discussion #2 (15 min) 
 ○ Participant experiences with group exercise, rating of perceived exertion ○ Graded steps to increase activity, time-based pacing (Graded Steps Handout) ○ I CARE video playlist, elicit other exercise options • Home exercise plan (15 min) 
 ○ Plan for week #1 (Home Exercise Worksheet; Readiness Rulers) ○ Share goals with group ○ Closing (5 min)
1.5	
Individual Session #1 (Virtual via Phone, 10-15 min)
 
 • MI: 
 ○ Readiness ruler ○ Self-efficacy, develop discrepancy ○ Amplify change talk, roll with resistance • Troubleshooting home activity plan 
 ○ Review safe space in home ○ Address level of activity, correct positions, etc.
2	
Group Session #2 (Virtual via Zoom, 90 min)
 
 • Discussion #1 (30 min) 
 ○ Elicit experiences with home activity goals (Self-Reflection Worksheet) ○ Physical activity, pain & fatigue (Activity, Pain & Fatigue Handout) • Group exercise (25 min) • Discussion #2 (15 min) 
 ○ Participant experiences with group exercise ○ Brainstorm strategies to address challenges, emphasize change talk

	
 • Home exercise plan (15 min) 
 ○ Plan for week #2 (Home Exercise Worksheet; Readiness Rulers) ○ Share goals with group ○ Closing (5 min)
2.5	
Individual Session #2 (Virtual via Phone, 10-15 min)
 
 • Troubleshooting home plan • MI: Self-efficacy, amplify change talk, roll with resistance
3	
Group Session #3 (Virtual via Zoom, 90 min)
 
 • Discussion #1 (15 min) 
 ○ Elicit experiences with home activity goals (Self-Reflection Worksheet) • Group exercise (25 min) • Discussion #2 (30 min) 
 ○ Participant experiences with group exercise ○ Physical activity and sleep (Better Sleep Guidelines and Worksheet) • Home exercise plan (15 min) 
 ○ Plan for week #3 (Home Exercise Worksheet; Readiness Rulers) ○ Share goals with group ○ Closing (5 min)
4	
Group Session #4 (Virtual via Zoom, 90 min)
 
 • Discussion #1 (20 min) 
 ○ Elicit experiences with home activity goals (Self-Reflection Worksheet) ○ Elicit experiences with sleep changes (Better Sleep Worksheet) • Group exercise (25 min) • Discussion #2 (20 min) 
 ○ Participant experiences with group exercise ○ Review physical activity, pain, fatigue, and sleep concepts • Home exercise plan (15 min) 
 ○ Plan for next 4 weeks (Home Exercise Worksheet; Readiness Rulers) ○ Share goals with group • Closing statements (10 min)
4.5	
Individual Session #3 (Virtual via Phone, 10-15 min)
 
 • Troubleshooting home activity plan for next month • MI: Self-efficacy, amplify change talk, roll with resistance
5-8	
Individual Sessions #4-7 (Virtual via Phone, 10-15 min, weekly)
 
 • Troubleshooting home activity plan • Gradually increase activity goals • MI: Self-efficacy, amplify change talk, roll with resistance
16	
Final In-Person Assessment (60 min)
 
 • Post-intervention Assessments: 
 ○ Physical functioning (VR-36,^{56,57} 6-minute walk,^{58,59} and 30-second sit to stand^{59,60}) ○ Other study measures* • Disconnect Garmin Vivosmart 4 device from I CARE Study account

*PTSD symptoms (PTSD Checklist for DSM-5 [PCL-5]^{61,62}); depressive symptoms (Patient Health Questionnaire-8 [PHQ-8]⁶³); pain (brief 3-item scale on intensity and interference [PEG]⁶⁴); fatigue (PROMIS 4-item fatigue short form⁶⁵); sleep quality (PROMIS sleep disturbance and impairment)^{66, 67}; self-efficacy (PROMIS general 4-item⁶⁸ and one item specific to physical activity); and social support for physical activity (1 item).
